The purpose of this study is to determine if apoC-III reduction using an ASO to apoC-III (ISIS 304801) will reduce triglycerides and improve insulin resistance, diabetes, and hepatic steatosis in patients with lipodystrophy. The primary hypothesis to be tested is:

1. ISIS 304801 will reduce log₁₀ fasting serum triglycerides.

Secondary and tertiary hypotheses to be tested are:

2. ISIS 304801 will improve glucose metabolism by improving insulin resistance.
3. ISIS 304801 will reduce hepatic steatosis.
4. ISIS 304801 will improve cardiovascular risk markers.

We will also explore the mechanism of action of apoC-III ASO by studying lipoprotein lipase activity and lipoprotein particle distribution.

Methods

This study will enroll up to 20 patients with partial lipodystrophy with a goal of 10 study completers. The study will be conducted in two phases. The first is a 16-week, randomized, double-blind, placebo-controlled design. Subjects will be treated with ISIS 304801 at a target dose of 300 mg per week or placebo. Following this phase, all subjects will enter a 12 month open-label extension in which they will receive active drug. Patients who experience benefit (triglyceride lowering $\geq 50\%$) may receive an additional 12 months of open-label drug (up to 24 months, total). Measurement of the primary outcome (serum triglycerides) and key secondary outcomes will be performed at baseline prior to the intervention, after 16 weeks (primary and secondary outcomes) of blinded drug or placebo, and after an additional 4 months of active drug in subjects initially randomized to placebo.

STUDY GLOSSARY

Abbreviation	Definition
2'-MOE	2'-O-(2-methoxyethyl)
AE	adverse event
ALT	alanine aminotransferase (SGPT)
ANA	antinuclear antibody
apoA1	apolipoprotein A1
apoB	apolipoprotein B
apoC-III	apolipoprotein C-III
apoE	apolipoprotein E
aPTT	activated partial thromboplastin time
ASO	antisense oligonucleotide
AST	aspartate aminotransferase (SGOT)
BMI	body mass index
BP	blood pressure
DEXA	dual-energy X-ray absorptiometry
DSMB	Data and Safety Monitoring Board
EKG	electrocardiogram
eCRF	electronic Case Report Form
FPG	fasting plasma glucose
FPL	familial partial lipodystrophy
FSH	follicle-stimulating hormone
GCP	Good Clinical Practice
HBsAg	hepatitis B surface antigen
HBV	Hepatitis B virus
HbA1C	Hemoglobin A1C
HCV	hepatitis C virus
HDL-C	high-density lipoprotein cholesterol
hERG	human ether-a-go-go
HIV	human immunodeficiency virus

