data from our group showed that elevated apoC-III plays a role in the hypertriglyceridemia seen in both generalized lipodystrophy and PL and might therefore represent a therapeutic target in these patients.

These data show (left graph) that apoC-III is significantly higher in lipodystrophy patients compared to age, sex, and race matched obese controls (30.4 ± 22.7 mg/dL in lipodystrophy versus 16.1 ± 6.9 in controls, $p < 0.0001$). In addition, apoC-III levels are very strongly correlated with triglyceride levels in patients with lipodystrophy (right graph, $R^2 = 0.52$, $p < 0.0001$), such that an elevated triglyceride level is highly predictive of an elevated apoC-III level.

By reducing apoC-III and TG levels, ISIS 304801 may improve the metabolic profile of patients with PL and reduce their risk of acute pancreatitis. In addition, apoC-III inhibition may also improve insulin sensitivity in these patients and potentially lead to a reduction in the complications associated with diabetes. It is unknown whether this mechanism could improve hepatic steatosis and reduce cirrhosis risk.

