2.3 ISIS 304801

2.3.1 Mechanism of Action

ISIS 304801 is a second-generation antisense oligonucleotide (ASO) drug targeted to human apoC-III. It is complementary to a region within the 3' untranslated region of the apoC-III mRNA and binds to the mRNA by Watson and Crick base pairing. The hybridization (binding) of ISIS 304801 to the cognate mRNA results in the RNase H-mediated degradation of the apoC-III mRNA, thus preventing production of the apoC-III protein. Maximal antisense-mediated reduction of target mRNA levels is typically greater than 90% of control levels in sensitive tissues^{35,36}. Furthermore, reduction in target mRNA levels using this approach correlates directly with a subsequent reduction in target protein levels.

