4.1 Design/Randomization

This study has two components. Initially, subjects will receive ISIS 304801 or placebo, in a 1:1 randomized, double-blinded fashion for 16 weeks. Randomization will occur after verification that all eligibility criteria have been met. The randomization will be stratified by use of lipid-lowering medications. After completion of 16 weeks, all subjects will receive ISIS 304801 for 12 months in an open-label extension (OLE) phase. After discontinuation of ISIS 304801 (due to study end or any other reason) subjects will be followed for an additional 12 week withdrawal phase when possible. Patients who experience benefit (triglyceride lowering $\geq 50\%$) may receive an additional 12 months of open label drug (up to 24 months, total). This period may initiate immediately following the standard 12 month OLE, or following the withdrawal phase.

- 1° outcome (Δ in log₁₀ triglycerides):
 - C vs D
 - F vs G
- 2°/3° outcomes – within subject comparisons:
 - C vs E
 - F vs H
- Placebo vs drug comparisons
 - C vs H

1

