5.2 Statistical Methods for Data Analysis

Descriptive statistics such as mean and standard deviation (or median and interquartile range) will be used to summarize data in raw scale or change from baseline per visit.

The primary outcome, change in log₁₀ TG at Week 16 from baseline, and continuous secondary outcomes will be compared between ISIS 304801 and placebo groups using either two-sample t-test or Wilcoxon rank sum test as appropriate based on change from Baseline at Week 16. Changes from baseline based on tertiary/exploratory outcomes as well as change on log₁₀ TG at Week 16 will be examined using either one-sample t-test or Wilcoxon signed rank test as appropriate.

Repeated measures analysis of covariance using linear mixed models will be conducted in order to investigate trends on selected response variables and to compare active and placebo group while possible covariates are taken into account. There are three possible covariates: (1) Baseline level of the outcome of interest, (2) Baseline level of ApoCIII, and (3) Change in ApoCIII before and after the 16 week active drug intervention.

Inclusion of covariates will be checked using linear mixed models by checking Akaike Information Criteria (AIC) with inclusion of one covariate at a time

Analyses will include all available data even if patients do not adhere to their assigned treatments. Additional analyses will examine the effect of adherence to study results. We will also investigate the effect of missing data on the results using standard methods for missing data.

A p-value of 0.05 or less is considered significant.

6. Experimental Plan

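### The mixed model comparing active with placebo may adjust for change in ApoC-III, the drug's own target, so its contrast need not be the treatment effect

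*Combined protocol and SAP*

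**What the plan says.** Section 5.2 gives one repeated-measures mixed model two jobs: to "investigate trends on selected response variables and to compare active and placebo group while possible covariates are taken into account". It then names three candidate covariates: the baseline of the outcome, baseline ApoC-III, and "3) Change in ApoCIII before and after the 16 week active drug intervention". Inclusion is to be checked by "Akaike Information Criteria (AIC) with inclusion of one covariate at a time".

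The main between-arm tests are separate. The primary outcome and the continuous secondary outcomes are compared "using either two-sample t-test or Wilcoxon rank sum test as appropriate based on change from Baseline at Week 16".

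On mechanism, section 2.3.1 says the drug degrades the apoC-III mRNA, "thus preventing production of the apoC-III protein". On timing, section 4.1 says "After completion of 16 weeks, all subjects will receive ISIS 304801 for 12 months in an open-label extension", and the Methods part of the Precis places a further assessment "after an additional 4 months of active drug in subjects initially randomized to placebo".

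**The concern.** Change in ApoC-III is a consequence of treatment and probably a step on the path from drug to triglycerides. Holding it fixed in a between-arm model asks what the drug does apart from lowering its target, which is not the randomised question. AIC gives no protection: it rewards fit and takes no account of whether a covariate precedes randomisation. The more strongly the mediator tracks the outcome, the more likely AIC is to select it.

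The window is a second difficulty. The covariate is defined by time on active drug, and placebo patients have none in the blinded period. Two readings are possible:

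- **Reading 1:** each patient's own first 16 weeks on drug, which for placebo patients ends at about Week 32. A Week 16 comparison is then conditioned on later open-label data.
- **Reading 2:** Weeks 0 to 16 in both arms. The comparison is then conditioned on a mediator.

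Neither is a baseline adjustment. What is at stake is the only covariate-adjusted active-versus-placebo comparison in section 5.2, for response variables that the plan does not name.

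**Working it through.** **The plan's own figure.** Section 5.1 gives 5 per arm, difference 0.50, SD 0.25 log10 mg/dL and two-sided 0.05. The noncentrality is (0.50/0.25) × √(5/2) = 3.162 on 8 df. The noncentral t gives power of 79.05%, matching the stated 79%. That figure is for the unadjusted comparison and is not in dispute.

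**Inputs for the illustration.** The on-drug change in ApoC-III is -15.3 mg/dL (SD 7.5), from the section 5.1 table; it comes from patients without lipodystrophy. Placebo change is assumed to be 0 with the same SD. The within-arm correlation r between change in ApoC-III and change in log10 TG is not in the documents, so a range is shown. Section 2.1 reports that "apoC-III levels are very strongly correlated with triglyceride levels in patients with lipodystrophy", with R² = 0.52. Its square root, 0.72, is cross-sectional rather than a correlation of changes; it serves as a high illustrative value, not a limit.

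**Reading 2, change in TG as the response.**

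- Adjusted contrast = -0.50 + b × 15.3, where b is the pooled within-arm slope.
- Same r in both arms: b = r × 0.25/7.5, so attenuation = r × (0.25/7.5) × 15.3/0.50 = 1.02r.
- Placebo-arm r of 0 and equal SDs: b is halved, so attenuation = 0.51r.

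| r | 0 | 0.3 | 0.5 | 0.72 |
|---|---|---|---|---|
| Contrast, same r in both arms | -0.50 | -0.35 | -0.25 | -0.13 |
| Attenuation | 0% | 31% | 51% | 73% |
| Contrast, placebo r = 0 | -0.50 | -0.42 | -0.37 | -0.32 |
| Attenuation | 0% | 15% | 26% | 37% |

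**Simulation at a single timepoint** (5 v 5, same r in both arms, 20,000 trials per value of r). This simplifies the mixed model to a Week 16 analysis.

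| r | 0 | 0.3 | 0.5 | 0.72 |
|---|---|---|---|---|
| Contrast with covariate forced in | -0.50 | -0.35 | -0.24 | -0.13 |
| Power with covariate forced in | 43% | 26% | 18% | 11% |
| AIC selects it over no covariate | 25% | 40% | 64% | 90% |
| Mean contrast after AIC choice | -0.50 | -0.38 | -0.28 | -0.15 |
| Power after AIC choice | 74% | 57% | 39% | 18% |

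At r = 0 there is no bias, but including the covariate still costs power because it is collinear with treatment. With placebo-arm r of 0, AIC selects the covariate in 26% / 29% / 37% / 48% of trials (40,000 per setting).

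**Repeated measures** (20,000 trials per setting, between-visit correlation 0.7 assumed; same r in both arms). The result depends on model form:

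- Change at four visits, treatment by visit plus a covariate main effect: -0.50 / -0.35 / -0.24 / -0.13.
- TG levels at Weeks 0 and 16 with a covariate-by-time term: -0.50 / -0.35 / -0.25 / -0.13.
- TG levels at Weeks 0 and 16 with a treatment-by-time contrast and no covariate-by-time term: -0.50 throughout.

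**Reading 1.** If mean on-drug change in ApoC-III is equal in the two groups, the adjustment term is b × 0 and the contrast stays at -0.50 for every r.

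**The case against.** The strongest reply is that little depends on this model. Every continuous primary and secondary outcome has its own unadjusted test, the covariates are only possible ones, and the AIC check requires fitting a model without them. The third covariate's wording suits an on-drug trend or mechanism analysis, which the protocol does intend. Reading 1 is also the closer fit to the wording: section 4.2.3 defines a comparison with the time just before treatment, and section 5.1 defines completion as 16 weeks on active drug. Under that reading there is no attenuation.

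The limit on scope stands in full. The rest does not remove the problem. Section 5.2 neither labels the model exploratory nor reserves this covariate for one of its two purposes, nor does it say which fitted model is reported. The first sentence of section 5.1 uses active-drug wording for the blinded comparison itself, so the window remains open. Reading 1 preserves the expected contrast only by bringing post-comparison data into it.

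The numerical objections are also fair:

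- With r = 0.5 in both arms, varying the placebo SD from 3 to 15 moves attenuation from 62% to 31%. With placebo r = 0 it moves from 44% to 10%.
- Using the lipodystrophy mean and SD in section 2.1 (30.4 and 22.7 mg/dL), a uniform fall of about 80% and equal SDs, attenuation is 20% / 33% / 48% at r = 0.3 / 0.5 / 0.72.
- If AIC picks the best of all three candidates, with the baselines unrelated to change, the third is chosen in 20% / 32% / 55% / 84% of trials at r = 0 / 0.3 / 0.5 / 0.72.

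These alter the size, not the principle.

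**Conclusion.** The concern holds and should be fixed. As written, the plan lets a fit criterion place a treatment-affected variable in a model whose stated uses include comparing the arms, and it leaves that variable's window undefined for placebo patients. Confidence is high in the principle and low in any particular size. Attenuation could be nil (Reading 1 with equal mean on-drug change, or TG levels without a covariate-by-time term). It could be about half at r = 0.5 in both arms under Reading 2 with change as the response, or more at higher r. Those figures rest on an unreported correlation, an assumed placebo mean and SD for ApoC-III change, and a model form that the plan does not fix. The defect does not reach the unadjusted primary and secondary tests.

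**What to change.** In section 5.2, remove change in ApoC-III from every model that compares active with placebo, leaving only baseline covariates there (baseline of the outcome and baseline ApoC-III). Use change in ApoC-III only in a separately labelled exploratory mechanism analysis, and state its start and end weeks for each arm.

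The cost is protocol and SAP wording, with no extra data or patients. Section 7.14 refers to samples already collected from enrolled patients, so the revision should record when it was made relative to unblinding. Two neighbouring matters are separate and remain after this change: AIC selection with a planned ten completers, and the absence of the stratification factor (lipid-lowering medication) from the covariate list.

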4.2 Outcome Measures

4.2.1 Primary outcome:

Efficacy of 16 weeks of ISIS 304801 as compared to placebo (between group comparison) on the change in log₁₀ fasting triglycerides (TG).

4.2.2 Secondary outcomes:

Efficacy of 16 weeks of ISIS 304801 as compared to placebo (between group comparison) on:

Lipids

- Percent change in fasting TG
- Absolute change in fasting TG
- Change in lipolysis rate measured using stable isotope tracers
- Change from baseline in liver volume and hepatic steatosis (as assessed by magnetic resonance imaging [MRI] and magnetic resonance spectroscopy [MRS])
- Lipoprotein lipase activity

Glycemic

- Change in total body insulin sensitivity using the hyperinsulinemic euglycemic clamp
- Change in hepatic glucose production and hepatic insulin sensitivity using stable isotope tracers in combination with the hyperinsulinemic euglycemic clamp
- Change in hemoglobin A1c (HbA1c)
- Change in fasting plasma glucose

Safety

- Safety and tolerability of ISIS 304801
- Prospectively adjudicated acute pancreatitis events (Atlanta classification) and Major Adverse Cardiovascular Events (MACE)

Pharmacokinetic

- Plasma ISIS 304801 level

4.2.3 Tertiary/Exploratory outcomes:

Efficacy of 16 weeks and 16 months of ISIS 304801 as compared to immediately prior to treatment (pre-post within subject comparison) on:

Lipids

- Change in other fasting lipid measurements: high-density lipoprotein cholesterol (HDL-C), low-density lipoprotein cholesterol (LDL-C), total cholesterol (TChol), very low-density lipoprotein cholesterol VLDL-C, non-HDL-C, apolipoprotein B (apoB), apolipoprotein B-48 (apoB48), apolipoprotein A1 (apoA1), apolipoprotein CIII (apoC-III; total, chylomicron, VLDL, LDL and HDL), and free fatty acids
- Change in lipoprotein particle size/number by nuclear magnetic resonance (NMR)
- Triglyceride (and other lipid particle) clearance following mixed meal testing

Glycemic

- Change in 24-h glucose (using 7-point plasma blood glucose)
- Change in fasting and area under the curve for insulin and C-peptide during mixed meal testing
- Reduction in insulin use

Adipose tissue

- Change in skinfold thickness and dual-energy X-ray absorptiometry (DEXA)
- Change in abdominal VAT and SAT volumes
- Change in adiponectin and leptin
- Change in body weight and waist circumference

Cardiovascular

- Carotid intima-media thickness (by ultrasound)
- Coronary artery wall thickness and diameter change after hand-grip exercise (by MRI)

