5.1 Sample Size Justification

The primary outcome variable is the change in log₁₀ fasting triglycerides from before treatment to 16 weeks of active drug treatment compared to placebo groups.

Preliminary data are available for 28 patients treated with ISIS 304801 and 24 treated with placebo. For the ISIS 304801 group, these data show a difference from baseline to follow-up of -423 (SD 400, 95% CI -578 to -268) mg/dL and -0.485 (SD 0.221, 95% CI -0.57 to -0.40) log₁₀ mg/dL. Converting the difference in log₁₀ mg/dL to a percent change [$100 \times (10^{-0.485} - 1)$] results in a percent change of -67% (95% CI -73% to -60%). For the placebo group, the absolute change is -12 (SD 406, 95% CI -12 to 184) mg/dL and -0.011 (SD 0.224, 95% CI -0.105 to 0.084) log₁₀ mg/dL. The percent change for the placebo group is -3% (95% CI -21% to 21%).

For comparison of placebo and ISIS 304801 we have chosen a SD of 0.25 log₁₀ mg/dL and a difference of 0.50 log₁₀ mg/dL. A trial with 5 patients in each group has 79% power to detect a difference of 0.50 log₁₀ mg/dL triglycerides in the change from baseline to follow-up between the ISIS and placebo groups, assuming a SD of 0.25 log₁₀ mg/dL and a two-sided significance level of 0.05.

Where preliminary data were available, sample size calculations were performed for secondary and tertiary study outcomes in addition to the primary outcome. The preliminary data and power estimates for a sample size of 10 subjects (using one-sample t-test for off versus on drug comparisons) are summarized in the table below. Based on these calculations, the study should be adequately powered to detect differences in total body insulin sensitivity, hepatic insulin sensitivity, fasting glucose, apoC-III serum level, HDL-C, VLDL-C, and apolipoprotein B48.

Based on these calculations, we plan to enroll a maximum of 20 patients, with a goal of 10 patients completing the study (defined as completing 16 weeks of active drug treatment). The accrual ceiling of 20 is planned because subjects will consent to the study prior to screening, thus we are accounting for up to 10 screen failures in the accrual ceiling.

	Outcome	Model	Treatment	Treat- ment Duration	Mean of Δ on-off drug (SD)	Power
Primary outcome	Absolute change log[serum triglycerides] (mg/dL)	High TG +/- diabetes and/or fibrate	ApoCIII ASO 300 mg/wk	16 wk	-0.48 (0.22)	>0.95
	% change serum triglycerides (%)	High TG +/- diabetes and/or fibrate	ApoCIII ASO 300 mg/wk	16 wk	-63 (20)	>0.95

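### The placebo comparisons of the secondary outcomes are listed both as secondary and as exploratory, and Section 5.2 calls any p of 0.05 or less significant, with no order, gate or adjustment

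*Combined protocol and SAP*

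**What the plan says.** - **Precis, Aim.** One primary hypothesis is named (a fall in log10 fasting triglycerides). Items 2 to 4, on glucose metabolism, hepatic steatosis and cardiovascular risk markers, follow under the words "Secondary and tertiary hypotheses to be tested are".
- **Section 4.2.2.** The between-group secondary outcomes include five lipid bullets and four glycemic bullets, all continuous. Two bullets hold two measures each. One pairs liver volume with hepatic steatosis. The other reads "Change in hepatic glucose production and hepatic insulin sensitivity using stable isotope tracers in combination with the hyperinsulinemic euglycemic clamp".
- **Section 4.2.3.** The tertiary/exploratory list is mainly within-subject, but its last line brings in the 16-week placebo comparison of the primary and the secondary outcomes.
- **Section 5.2.** In the same sentence as the primary, "continuous secondary outcomes will be compared between ISIS 304801 and placebo groups using either two-sample t-test or Wilcoxon rank sum test". The section closes with "A p-value of 0.05 or less is considered significant".
- **Section 5.1.** The primary is sized at "a two-sided significance level of 0.05", with 5 patients per arm.

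The supplied text gives no testing order, no condition that the primary succeed first, no split of alpha and no multiplicity adjustment. Sections 6.4.3 and 6.4.4 defer to a SAP, but only for pharmacokinetic and immunogenicity detail.

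**The concern.** The rule in 5.2 does not distinguish the one primary test from the nine to 11 secondary ones. The labels do not settle the matter, because the same contrast is secondary in 4.2.2 and exploratory in 4.2.3. The precis presents the metabolic and hepatic questions as hypotheses to be tested. Section 5.1 also describes the study as adequately powered for several of them, although that power comes from one-sample tests in 10 subjects and not from the comparison of 5 with 5 in 5.2.

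Followed literally, 5.2 lets a single chance result among many be reported as significant support for a stated hypothesis, even if the primary fails. What is at stake is the credibility of the secondary findings, chiefly those on glucose and insulin. The primary test of log10 triglycerides keeps its own 5% level.

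**Working it through.** **1. The plan's own figure.** Section 5.1 states "A trial with 5 patients in each group has 79% power". Its inputs are "we have chosen a SD of 0.25" "and a difference of 0.50" (both in log10 mg/dL) and two-sided alpha 0.05. The standardised difference is 0.50/0.25 = 2.0. A two-sample t-test with 5 + 5 − 2 = 8 degrees of freedom (noncentral t) has power 79.05%, so the 79% reproduces. The layout of 5 against 5 with t-tests is therefore the right basis for the secondaries too. Two-sided testing is stated for the primary and assumed here for the secondaries.

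**2. Counting the measures in 4.2.2.**
- Triglycerides, 2: percent change and absolute change. Both re-express the primary variable.
- Other lipid and liver, 4: lipolysis rate, liver volume, hepatic steatosis, lipoprotein lipase activity.
- Glucose and insulin, 5: total body insulin sensitivity, hepatic glucose production, hepatic insulin sensitivity, HbA1c, fasting glucose.

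The total is 2 + 4 + 5 = 11, or 9 without the two triglyceride measures. Nine is the more useful count: if all 11 are null, the primary is null too, whereas the nine can be null while the drug lowers triglycerides as expected.

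**3. Independent t-tests.** The chance of at least one p of 0.05 or less among k null outcomes is 1 − 0.95^k.
- k = 11: 1 − 0.95^11 = 0.431
- k = 9: 1 − 0.95^9 = 0.370
- k = 5: 1 − 0.95^5 = 0.226

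**4. Correlated outcomes.** The documents give no correlations, so a common correlation is assumed and varied. The figures come from simulated null trials (200,000 per setting), with equicorrelated normal outcomes in two arms of 5.

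| Chance of at least one significant result | 0 | 0.3 | 0.5 | 0.7 | 0.9 |
|---|---|---|---|---|---|
| 11 measures, t-test | 43% | 39% | 33% | 25% | 14% |
| 9 non-triglyceride measures, t-test | 37% | 34% | 29% | 22% | 13% |
| 5 glucose/insulin measures, t-test, either direction | 23% | 21% | 19% | 16% | 11% |
| 5 glucose/insulin measures, t-test, improvement only | 12% | 11% | 10% | 8% | 5% |
| 9 non-triglyceride measures, rank-sum | 25% | 23% | 20% | 16% | 10% |
| 11 measures, rank-sum | 30% | 27% | 23% | 18% | 11% |

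Columns are the assumed common correlation.

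**5. Why the rank-sum rows are lower.** With 5 against 5 there are 252 equally likely rank allocations. The largest two-sided rejection region within 0.05 holds 8 of them, so the exact level is 8/252 = 0.032 per test. For nine independent tests this gives 1 − (1 − 8/252)^9 = 0.252.

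**6. Whether a simple Bonferroni split would serve.** It would not. For 11 measures the level is 0.05/11 = 0.0045, and for nine it is 0.05/9 = 0.0056. The smallest two-sided p a rank-sum test can give at 5 against 5 is 2/252 = 0.0079, above both.

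**The case against.** The strongest reply is that this is a rare-disease trial aiming for about 10 completers, with one named primary outcome. Nothing in 5.2 says that a significant secondary is confirmatory, and how such results might later be cited is speculation. That limits the seriousness of the point but does not remove it: 5.2 still states a rule that attaches the word significant to each secondary result, and the precis frames the questions as hypotheses.

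Four stronger readings are tempting, and the documents do not support them.

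- **That the secondaries carry no exploratory label.** The last line of 4.2.3 places these same comparisons under an exploratory heading. Because that line also takes in the primary, it cannot be read as a deliberate downgrade of the secondaries. The supportable defect is a conflict of status that 5.2 leaves open.
- **That the false-positive rate is one known figure, such as 33%.** That value needs all 11 measures, t-tests throughout and a common correlation of 0.5. Section 5.2 also allows the rank-sum test, and no correlation is given. Only a range with its assumptions can be defended.
- **That a claim of better insulin resistance carries the rate for all 11.** It rests on five measures, and for a false claim of improvement the rate is about 5% to 12%.
- **That a steatosis claim can be made on any one of several measures.** Section 4.2.2 has one direct measure, hepatic steatosis by MRI and spectroscopy, with a 5% two-sided error. Adding liver volume, which is not steatosis, gives at most 1 − 0.95^2 = 9.75% two-sided, or about 5% in the favourable direction.

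**Conclusion.** The point holds in a bounded form. The placebo comparison of the secondary outcomes has two statuses, and 5.2 applies an unadjusted 0.05 rule to all of it. For the nine non-triglyceride measures, the chance of at least one false significant result lies between about 13% and 37% with t-tests (29% at correlation 0.5), which is roughly 2.6 to 7.4 times 5%. It lies between about 10% and 25% with rank-sum tests.

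These figures assume arms of 5, two-sided tests, normal outcomes, a common correlation from 0 to 0.9, one test used throughout, and no drug effect on the measures counted. They count results in either direction. Section 5.2 gives no criterion for choosing between the t-test and the rank-sum test, and any extra error from that choice is not included.

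This merits correction because the rule is stated and the remedy is short. It is not a threat to the primary analysis.

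**What to change.** 1. **Section 5.2.** Replace the closing rule with wording such as: Statistical significance, at two-sided 0.05, is claimed only for the primary contrast, drug against placebo in change in log10 triglycerides at Week 16. Secondary outcomes are presented as estimates with 95% confidence intervals and nominal p-values, are hypothesis-generating, and are not adjusted for multiplicity.
2. **Optional.** If one firm metabolic claim is wanted, name a single key secondary in advance (total body insulin sensitivity, for instance) and test it at 0.05 only if the primary is significant. That fixed order holds the error over the two tests at 5%.
3. **Precis and 4.2.2.** Relabel precis items 2 to 4 as exploratory, apart from any key secondary, and make 4.2.2 carry the same status.
4. **Section 4.2.3.** Delete or correct the last line, which puts the primary and secondary placebo comparisons under the exploratory heading.

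The cost is a few sentences and labels, with no added patients or data. The one loss is that an isolated secondary p of 0.05 or less can no longer be reported as significant.
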